AA: These patients will be recruited from the NYUBAR (N = 30) and advertising and will have asthma as defined by NIH guidelines (51), persistent symptoms, and absence of WTC dust exposure.

Control: These patients will be recruited from the NYUBAR (N = 30) and advertising and will have no respiratory sx, no asthma diagnosis, no WTC dust exposure. Additional appropriate inclusion and exclusion criteria will be developed for each group including tobacco use, other lung disease, timing of inhaled corticosteroids etc.

The study will entail two to three visits. On visit 1 (V1) all individuals will sign informed consent to participate in the study under an NYU IRB approved protocol. A questionnaire will be completed with standardized questions that include information on WTC exposures, demographics, presence and severity of respiratory symptoms, tobacco history and past medical history. Individuals will undergo spirometry with inhaled bronchodilator. Individuals will undergo methacholine challenge test (visit 1a) if they have normal spirometry or no bronchial hyperresponsiveness. On visit 2, individuals will return to undergo ENO, EBC and spirometry with pre and post bronchodilator maneuvers and induced sputum. Blood will be obtained for CBC with differential cell count, and assessment of total IgE and allergen-specific IgE. Blood will also be stored for future analysis of inflammatory markers. Based on our experience, we have had individuals unable to produce enough sputum and thus yield too small a number of cells. These individuals are excluded from data analysis. In addition, we also have subjects who are able to produce sputum and return for repeat sputum testing.

SA1.b We will measure biomarkers of inflammation using noninvasive techniques for exhaled nitric oxide (ENO) and 8-isoprostanate from exhaled breath condensate (EBC) in WTC IA, AA and controls.

We will use the handheld NIOX MINO® to measure ENO (Aerocrine, Sweden) (17, 18, 20, 52). The NIOX MINO® fulfills the ATS recommendations and provides reliable readings and is portable and we have experience with it (53). Most healthy individuals have ENO levels in the range of 5-35 ppb (some variation with age, gender, race/ethnicity) (54). Individuals with asthma have ENO levels that can range from 25-80 ppb and even higher (18, 61, 62).

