EBC will be collected using a commercially manufactured condenser R tube® (Respiratory Research, Inc., Charlottesville, VA) for this study because of its transportability and price. Again, we have experience with this technique. Measurements will be made according to published methods (28). Samples will be transported immediately

and frozen (-70° C) to improve stability. Our initial studies will focus on measurements of 8-isoprostanate, a reliable biomarker of oxidative stress (24, 64). 8-isoprostanate will be measured by commercially available ELISA. We will also measure pH of EBC (28, 67). EBC pH is reduced in individuals with asthma and COPD. Changes in pH may be used as diagnostic and monitoring modalities in inflammatory airway diseases (68). We will measure pH in degassed samples as described (69). Samples will also be stored for future studies of inflammatory mediators including cytokines/chemokine studies.

SA1.c We will measure inflammatory cells in induced sputum from individuals with IA, AA and Controls.

Increased numbers of eosinophils and neutrophils have been identified in IS in allergic asthma and occupational asthma and have been used to monitor asthma disease activity (31, 33, 34, 36, 70). We propose to perform sputum induction, collection and processing according to established protocols on each individual (71, 72). IS will be collected after inhalation of hypertonic saline (3%, every 2 minute intervals for up to 20 minutes) with repeated monitoring of FEV₁ as a safety measure. Sputum will be processed immediately to obtain total and cell differential cell counts (73). Our initial evaluation included analysis of cell counts, with measurements of eosinophils and neutrophils (Bleck et al., 2015). We consider significant sputum eosinophilia when sputum eosinophils are $\geq 2\%$ and significant sputum neutrophilia when sputum neutrophils are $\geq 60\%$, cut off values, that have been described in the literature (12). We will also examine cell counts as continuous variables.

Specific Aim 2: To test the hypothesis that the miRNA expression in airway epithelial cells will differ between IA, AA and Control individuals.

SA2.a. We will isolate RNA from epithelial cells and inflammatory cells in induced sputum and nasal brushing and assess the miRNA and mRNA target genes and expression profile using microarray technology among individuals with IA, AA and Controls.

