We were able to develop basic techniques and measurement from 10 patients in each group as initially proposed in the previous version of this protocol. We now propose to increase our enrollment from 30 to 50 subjects in each group based on the recruitment and enrollment data of about 30% of screen failures (33 subjects screen failed out of 108 total). In addition, there have been subjects who have not been able to produce sputum or provide adequate number of sputum cells for analysis (38 subjects out of 65 accrued gave adequate sputum samples). This represents about 60% success rate for sample quality. Therefore, we will need to increase our enrollment numbers to achieve an n=30 per group.

Power Analysis: Based on a similar rate of screen failures and inadequate samples, the analysis is now based on 50 patients in each group. Our group sample sizes of 50 and 50 achieve 90% power to detect a difference of 0.73 given the null hypothesis that the two-group difference is 0 and the estimated group standard deviations are 1.0 and 1.0, with a significance level (alpha) of 0.05 using a two-sided two sample t-test. We will work with [name], our biostatistician for our statistical analysis.

For ENO and EBC analyses, we will express data as means \pm SD for normally distributed variables. For variables that are not normally distributed we will use medians and the interquartile range. We will use statistical analysis including unpaired *t* tests, Kruskal-Wallis test, and regression coefficients as appropriate. P values of < 0.05 will be considered significant. Differential expression of miRNA and hierarchical clustering will be performed with the genomics core. Statistics using *t* tests or algorithms designed specifically for data mining and biochip interpretation will be used. Pathway analyses will also be performed by the genomics computational core.

Anticipated results and alternative approaches

We will continue to recruit patients with WTC exposure or with asthma based on our experience in our asthma registry or our WTC clinic, in which most people are willing and anxious to participate in any study that might help characterize their symptoms.

We plan to also submit an advertisement to the IRB for approval and to use research match (researchmatch.org) a national registry which is a secure, web-based approach as a recruitment method, and will post the advertisement.

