We have chosen to use individuals with WTC dust cloud exposure as our model of initial high dose exposure to enhance our ability to identify patients with irritant asthma. We suspect that other more prolonged exposures also induce irritant asthma, but our previous studies and those of other investigators suggest that this exposure provides the highest risk.

We have proposed a positive selection strategy for isolation of bronchial epithelial cells from IS. The possibility exists that this technique may provide too low a yield of cells. Should that be the case, we can use a negative selection strategy using anti-CD14 and anti-CD16 antibody beads to specifically deplete macrophages and neutrophils respectively (37). We may also need to obtain duplicate sputum samples from patients, i.e. have patients return for a second sputum induction.

Our initial analyses will be between our healthy controls and asthma in general (AI and AA) and subsequently between each type of asthma (AI and AA) to optimize our ability to detect differences in sputum markers and miRNA. The

possibility exists that we will find no difference between measurements of markers of inflammation in exhaled breath between AI and AA. Should that be the case, we will have to examine whether our pilot study was powered to identify a small difference.

We are basing our miRNA and mRNA studies on those that have been performed in epithelial cells derived from cigarette smokers (45). These studies have shown a correlation between mRNA and miRNA expression and thus there is precedent for our studies. Because of the high price of each of these chips, and the cost of core analysis time, we initially propose to use 5 subjects for each condition to obtain a global pattern scale. These studies will subsequently be extended to get a reasonable statistical power.

From our pilot studies and recent publication we will continue to investigate mechanisms of asthma and irritant-induced asthma. The studies are high risk but have potential for high yield, and will provide data for subsequent NIH applications for replication and further evaluation for a junior faculty member. In addition, they have potential to provide information that could help target specific interventions for asthma of different phenotypes as we proposed in phase II of the study. As such, they fit the mandate of the CTSI grants.

II. Characteristics of the Research Population

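### The exclusion for inadequate sputum is not limited to sputum endpoints; applied as written, it would drop about 41.5% of participants from the ENO and EBC analyses, which need no sputum

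*Combined protocol and SAP*

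**What the plan says.** All references are to the combined protocol and SAP.

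- **Visit schedule (SA1.a).** "On visit 2, individuals will return to undergo ENO, EBC and spirometry with pre and post bronchodilator maneuvers and induced sputum". Blood is taken as well. The schedule is the same for all participants.
- **Exclusion (SA1.a, same paragraph).** After noting that some people produce too little sputum and so too few cells, the text says: "These individuals are excluded from data analysis". The next sentence concerns people who come back for repeat sputum testing.
- **SA1.b outcomes.** ENO is read on a handheld device. 8-isoprostane is measured in EBC collected with a condenser tube, and "We will also measure pH of EBC". None of these uses sputum.
- **Statistical Analysis.** The experience to date is "38 subjects out of 65 accrued gave adequate sputum samples", described as about 60% success. The loss is described as failure to "provide adequate number of sputum cells for analysis". Hence "we will need to increase our enrollment numbers to achieve an n=30 per group", while the power statement says "the analysis is now based on 50 patients in each group".
- **ENO/EBC analysis paragraphs** (Statistical Analysis, and section III.2, Data Analysis and Data Monitoring). They give summaries and tests but name no analysis population.
- **Headcounts.** Section II, item 1 counts 90 subjects as those who can produce sputum. Subject Capacity, in the consent section, counts 90 as those accrued who can enter the data analysis.

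**The concern.** The rule removes people, not samples, and does not say which analyses it covers. It stands in SA1.a, before the exhaled-breath outcomes (SA1.b) and the sputum cell counts (SA1.c) are separated. An analyst following it literally would delete valid ENO and EBC results because of a failed sputum induction.

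The stake is precision in SA1.b. Aim 1 asks whether irritant asthma resembles allergic asthma in its inflammatory markers, so the width of the interval for the difference between the two asthma types matters. The section on anticipated results foresees no difference in exhaled-breath markers between those types, and says the team would then ask whether the pilot could have detected a small one. Discarding about two in five available measurements makes that question harder to answer.

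**Working it through.** **1. Share affected.** The inputs come from Statistical Analysis: 65 accrued, 38 with adequate sputum.
- Adequate: 38/65 = 58.5%, which agrees with the stated figure of about 60%.
- Not adequate: 27/65 = 41.5%.

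This assumes that all 27 fall under the rule. The rate is pooled over the three groups.

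**2. Formulas.** SD is 1, alpha is 0.05 two-sided, and the test is a two-sample *t*-test, as in the power statement. The difference of 0.73 SD is that statement's generic value, not an ENO or EBC effect.
- Power: noncentral *t* with n1 + n2 − 2 degrees of freedom and noncentrality 0.73 / √(1/n1 + 1/n2).
- 95% CI half-width: t(0.975, n1 + n2 − 2) × √(1/n1 + 1/n2). It does not depend on 0.73. For 30 v 30: 2.002 × 0.2582 = 0.52. For 50 v 50: 1.984 × 0.2000 = 0.40.

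The protocol states 90% power for 50 per group at 0.73. This formula gives 95.1%. That mismatch is a separate matter. The recomputed value is used below so that both sides of each comparison are on the same footing.

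**3. Assumption 1: 50 accrued per group, 30 with adequate sputum** (50 × 0.60 = 30).

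| Quantity | Rule applied to ENO/EBC | Everyone measured |
|---|---|---|
| Pairwise power at 0.73 SD | 79.4% (30 v 30) | 95.1% (50 v 50) |
| Pairwise 95% CI half-width | 0.52 SD | 0.40 SD |
| Pairwise difference detectable with 80% power | 0.74 SD | 0.57 SD |
| Power, controls v pooled asthma | 89.8% (30 v 60) | 98.7% (50 v 100) |

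**4. Assumption 2: the 300 consents in section II, item 1, split equally (100 per group).** The counts in Statistical Analysis do not add up: 108 screened less 33 screen failures is 75, but 65 are called accrued, so 10 people are unexplained. Both treatments are shown.

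| Treatment of the 10 | Accrued per group | Adequate sputum per group | Power, rule v everyone | Half-width, rule v everyone |
|---|---|---|---|---|
| Reported counts | 100 × 65/108 = 60.2 (60) | 100 × 38/108 = 35.2 (35) | 85.3% v 97.8% | 0.48 v 0.36 SD |
| The 10 assumed accrued | 100 × 75/108 = 69.4 (69) | 69.4 × 38/65 = 40.6 (41) | 90.4% v 98.9% | 0.44 v 0.34 SD |

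The documents do not make clear whether the 300 also counts Phase II consents.

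**5. Further EBC samples to assay if everyone is kept, over three groups.**
- Assumption 1: 3 × (50 − 30) = 60.
- Reported counts: 3 × (60.2 − 35.2) = 75.
- The 10 assumed accrued: 3 × (69.4 − 40.6), about 87.

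**The case against.** The strongest reply is that the sentence was never meant to reach ENO or EBC. It sits between two sentences about sputum, its reason is too few cells, and it opens from past experience rather than as a formal definition of an analysis set. Statistical Analysis describes the same loss in terms of sputum cells, and the ENO/EBC paragraphs impose no sputum condition. The two counts of 90 are headcount entries; neither mentions ENO or EBC, and the one in section II covers both phases. All of this stands. It makes a sputum-only intent plausible, and under that reading no data are lost. It does not settle the question, because no section limits the rule and the headcounts are consistent with the broad reading.

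A reader might infer two stronger things that the documents do not support:
- **That the study would miss its planned size.** Thirty per group is the protocol's own target after sputum loss, so keeping 30 is not a shortfall against it.
- **That the ENO and EBC comparisons would be biased.** Sputum adequacy is reported only pooled over groups, so the direction and size of any bias cannot be judged.

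It is also fair to say that the study is a pilot, that the controls v pooled asthma comparison comes first and keeps 89.8% power under Assumption 1, and that a second induction may lower the 41.5%.

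**Conclusion.** The point holds conditionally. The text contains an unrestricted exclusion that, if applied as written, would needlessly discard SA1.b data on about 41.5% of participants. In each scenario the 95% CI half-width for a pairwise comparison is about 30% larger (0.52 v 0.40, 0.48 v 0.36 and 0.44 v 0.34 SD), and this does not depend on the assumed effect. The power figures are illustrations at a generic 0.73 SD. All sizes rest on the past pooled adequacy rate and on the assumed numbers per group. Whether the loss would occur depends on an intent that the documents do not state, so confidence is medium. The text should be corrected under either reading.

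**What to change.** Three wording changes:

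1. **SA1.a:** say that participants without an adequate sputum sample are excluded from sputum cell and sputum RNA analyses only.
2. **Both ENO/EBC analysis paragraphs** (Statistical Analysis and section III.2): say that these analyses include all eligible participants with the measurement, whether or not their sputum was adequate. Changing SA1.a alone would still leave these analyses without a stated population.
3. **Headcounts** (SA1.a, section II item 1, Subject Capacity): label the 90, or 30 per group, as the target for sputum endpoints.

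Repeating the ENO and EBC analyses in participants with adequate sputum would be a reasonable optional sensitivity analysis.

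Cost: no new visits or procedures. ENO is read directly, and EBC is already scheduled for everyone at visit 2. The added work is 8-isoprostane ELISA and pH on about 60 to 87 further EBC samples. The documents give no assay costs. If sputum-only was always meant, these assays were already implied and the change is editorial.

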Specific Aim 1: To test the hypothesis that irritant-induced asthma is characterized by elevated markers of inflammation in a manner similar to that described for allergic asthma.

SA1.a We will identify and phenotype individuals with WTC dust cloud-exposed irritant-induced asthma (IA), individuals with allergic asthma (AA) and healthy unexposed individuals (Controls).

SA1.b We will measure biomarkers of inflammation using noninvasive techniques for exhaled nitric oxide (ENO) and 8-isoprostanate from exhaled breath condensate (EBC) in WTC irritant-induced asthma (IA), individuals with allergic asthma (AA) and in healthy unexposed individuals (Controls).

SA1.c We will measure inflammatory cells in induced sputum from individuals with IA, AA and Controls.

Specific Aim 2: To test the hypothesis that the miRNA expression in airway epithelial cells will differ between IA, AA and Control individuals.

SA2.a. We will isolate RNA from epithelial cells and inflammatory cells in induced sputum and assess the miRNA expression profile using microarray technology among individuals with irritant-induced asthma (IA), individuals with allergic asthma (AA) and healthy unexposed individuals (Controls).

SA2.b. We will identify the mRNA targets of the differentially expressed miRNAs by using publicly available databases and correlate miRNA and mRNA expression.

Specific Aim 3: To test the hypothesis that levels of RNA of targets in human sputum cells will differ before and after the administration of inhaled corticosteroids in asthmatics (both IA, AA). The importance of this hypothesis in the characterization of irritant induced and allergic asthma is to further characterize the regulatory pathways expressed in sputum cells by identifying which inflammatory markers are steroid sensitive and steroid resistant.

SA3.a. We will isolate RNA targets in discrete sputum cells from induced sputum in IA and AA individuals and compare levels before and after administration of inhaled corticosteroids.

I. Background and Significance

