Most miRNA bind to target-3'UTR and function as translational repressors most often by promoting the degradation of mRNA. Each miRNA may regulate up to 200 target genes (42). We therefore propose to correlate patterns of miRNA changes in our defined populations, with mRNA expression arrays. HMW RNA from isolated epithelial cells will be used for hybridization to Affymetrix HG-U133 Plus 2.0 microarrays. Images will be analyzed in the core facility and data will be normalized as follows: (1) per array, by dividing the raw data by the 50th percentile of all measurements; and (2) per gene, by dividing the raw data by the median expression level for all the genes across all arrays in a data set. We will determine whether up or down-regulated mRNAs are potential targets for previously identified miRNAs.

Specific Aim 3: To test the hypothesis that levels of RNA of targets in human sputum cells will differ before and after the administration of inhaled corticosteroids in asthmatics (both IA, AA). The rationale for this aim of the study is to

investigate which markers are steroid sensitive and which are steroid resistant which would provide information for therapeutic targeting in asthma.

SA3.a. We will isolate RNA targets in discrete sputum cells from induced sputum in IA and AA individuals and compare levels before and after administration of inhaled corticosteroids.

In this second phase of the study, (Phase II) we will enroll AA or IA individuals who have fit enrollment criteria for the phase I part of the study and participated in phase I of the study and were able to provide us with an acceptable sputum sample. These participants will be recontacted for participation in Phase II if they signed permission to be re-contacted. We will obtain a repeat sputum sample as baseline for the Phase II study. An inhaled corticosteroid (Fluticasone HFA 220 mcg, 1 puff twice daily) and large volume spacer will be provided. Inhalation technique and a daily diary will be reviewed. Subjects will be instructed to use Fluticasone propionate 220 mcg q puff twice daily and to record their use in a written diary. A repeat sputum sample will be obtained after 2 weeks of Fluticasone propionate use.

Sputum samples will be processed for discrete cells and RNA levels (mRNA, miRNA) will be analyzed to understand the effect of ICS use on RNA expression in discrete sputum cell populations.

Statistical Analysis:

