The use of sputum for molecular genetic analyses is limited by its cellular heterogeneity which includes 1% of bronchial epithelial cells and greater than 95% macrophages and neutrophils (74). Enrichment of bronchial epithelial cells has been achieved by magnetic cell sorting (MACS). We will perform positive selection of discrete sputum cell populations including epithelial cells and dendritic cells using magnetic bead preparations or via flow cytometry. Human epithelial cells will be purified from sputum according to the expression of CD326 (human epithelial antigen, HEA, or epithelial cell adhesion molecule (EpCAM) using the magnetic bead CD326 (EpCAM) Tumor Cell Enrichment and Detection Kit (Miltenyi Biotech). To confirm purity of our isolation for selected samples, epithelial cell identification will be demonstrated by intracellular pan-cytokeratin staining. Cells will immediately be placed in RNAProtect Cell Reagent (QIAGEN) and RNA isolated and fractionated into low molecular weight (LMW) and high molecular weight (HMW) using the miRNeasy mini kit (QIAGEN). RNA will be quantified and quality assessed. We will collaborate with the NYU Cancer Institute (CI) Genomics Services. We will have access to high-throughput genomic and computational methodologies specifically for microRNA. We will use the GeneChip® miRNA Array. Briefly, LMW RNA will be labeled with a FlashTag labeling kit (Genisphere, Inc.) according to the manufacturer's protocol. Samples will be incorporated into a hybridization mix and applied to an affymetrix chip and scanned. Computational analysis with techniques such as principal component analysis will be performed with analytic services provided through the NYU CI Genomics core facility. Data will be log transformed and only miRNA replicates that are detected at levels of 2 standard deviations above the average background will be considered for further analysis. These studies will provide us with distinct miRNAs that may differ between IA, AA and controls, or IA and AA. If specific miRNAs are identified that are different between IA, AA and controls, or IA and AA, we will further validate expression of the miRNA using quantitative real time PCR.

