We will obtain epithelial cells from the lining of the nose using a technique called nasal brushing. This is a simple, nonsurgical procedure and is well tolerated by most people. We will gently brush the inside of the lateral wall of each nostril with a small, delicate, sterile brush. This procedure takes about 5 seconds for each nostril.

We also propose to correlate patterns of miRNA changes in our defined populations, with mRNA expression arrays. HMW RNA from isolated epithelial cells will be used for hybridization to Affymetrix HG-U133 Plus 2.0 microarrays. Images will be analyzed in the core facility and data will be normalized as follows: (1) per array, by dividing the raw data by the 50th percentile of all measurements; and (2) per gene, by dividing the raw data by the median expression level for all the genes across all arrays in a data set. We will determine whether up or down-regulated mRNAs are potential targets for previously identified miRNAs.

Phase II

Only subjects with Irritant asthma or Allergic asthma who have successfully completed the first phase of the study and have signed consent to be re-contacted will be recruited for the second phase of the study (Phase II). Phase II will involve two visits over a 2 week time period. For Phase II, we will first obtain sputum samples for a baseline analysis of cells. Study subjects will be provided with an inhaled corticosteroid, Fluticasone propionate HFA 220 mcg, 2 puffs twice a day (Treatment), or no treatment (No treatment). Fluticasone HFA will be provided by the study physician through the CTSI and the Bellevue Pharmacy. Treatment cases will be instructed to self administer the medication with a large volume spacer that will be provided to them. Inhaler teaching will be performed by study physician or coordinator at the time that the subject is provided the inhaler. Treatment Cases and No treatment controls will be provided a diary to record fluticasone inhaler. Treatment cases and No treatment controls will be allowed to use their usual rescue bronchodilator (albuterol) on an as needed basis. Treatment Cases and No treatment controls will return after 2 weeks for a repeat sputum induction.

2. Data Analysis and Data Monitoring:

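### Aim 3 states an uncontrolled before-after comparison, although Phase II has an untreated group; for miRNA and non-epithelial RNA no other Phase II comparison is stated

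*Combined protocol and SAP*

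**What the plan says.** The combined protocol and SAP describes Phase II in two ways.

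**Specific Aims, and Research Design and Methods under Specific Aim 3.** The hypothesis is that "levels of RNA of targets in human sputum cells will differ before and after the administration of inhaled corticosteroids". SA3.a will "compare levels before and after administration of inhaled corticosteroids". The stated purpose is to "investigate which markers are steroid sensitive and which are steroid resistant". The procedures there take a baseline sputum, supply fluticasone, and continue: "A repeat sputum sample will be obtained after 2 weeks of Fluticasone propionate use". No untreated group is mentioned. The analysis is put as "RNA levels (mRNA, miRNA) will be analyzed to understand the effect of ICS use on RNA expression in discrete sputum cell populations".

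**Section III.1, Phase II.** Participants get fluticasone, "2 puffs twice a day (Treatment), or no treatment (No treatment"), and "Treatment Cases and No treatment controls will return after 2 weeks for a repeat sputum induction".

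**Section III.2, Data Analysis and Data Monitoring.** The primary outcome is the change in epithelial TSLP expression on steroid relative to no treatment. Two randomised groups are compared by a two-group t-test, or by a Wilcoxon test if the data are skewed. The next sentences add, as an exploratory goal, the steroid effect on newly identified epithelial targets from the expression array, with no comparator named. The sample-size statement is 15 and 15, 1.3 SD, alpha 0.01, 80% power.

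Section III.1 also says which cells are sorted: "positive selection of discrete sputum cell populations including epithelial cells and dendritic cells".

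**The concern.** One description is a single-arm study and the other a two-arm study, and both stand in current text. They differ on dose as well (one puff twice daily under SA3.a, two puffs in section III.1), so the SA3.a text has not been brought into line with section III.

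The consequence falls on the RNA targets that the Phase II paragraph of section III.2 does not reach. That paragraph covers TSLP and array targets in epithelial cells. It mentions neither miRNA nor dendritic or other non-epithelial cells, although SA3.a promises both RNA types in several sorted populations. For these, a reader who looks for the planned comparison finds only SA3.a.

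A change seen only in treated participants mixes the drug effect with anything else that moves over two weeks, including the effect of a second sputum induction. A marker could be labelled steroid sensitive because of a shift that untreated participants share. It could also be labelled resistant because an opposing shift hid a real fall. Sorting markers this way is the purpose of Aim 3.

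**Working it through.** **Which text covers which target**

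| Phase II target | Comparison stated in III.2 | Comparison stated in Aim 3 / SA3.a |
|---|---|---|
| TSLP, epithelial cells | Change, steroid against no treatment, randomised groups | Before-after |
| Array targets, epithelial cells | Effect to be examined; comparator not named, but the sentence follows the randomised comparison | Before-after |
| miRNA | None specific to Phase II | Before-after |
| RNA in non-epithelial cells | None | Before-after |

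The gap is the last two rows.

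**The plan's own figure.** Two-sample t-test, 15 per group, d = 1.3, two-sided alpha 0.01. Noncentrality = d × √(n/2) = 1.3 × √7.5 = 3.56, with 28 degrees of freedom and critical value 2.763. Power is 0.780 by the exact noncentral t and 0.838 by the normal approximation. The difference detectable with 80% power is 1.327 SD, which rounds to the stated 1.3. The figure is reproduced, and it belongs to the between-group design.

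**Illustration of the bias.** The plan names no within-arm test and gives no size for a non-drug shift. Assumed here: a paired t-test in the treated arm; n = 15 and alpha 0.01, borrowed from the sample-size statement; all effects in SD of the within-person change. Let δ be the drug effect and s a shift common to both arms.

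- Within arm: the test sees δ + s. Noncentrality = (δ + s) × √15, 14 degrees of freedom, critical value 2.977.
- Between groups: the test sees (δ + s) − s = δ, so the shift cancels.

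*False positives (δ = 0)*

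| s | (s × √15) | Within arm | Between groups (simulated, 200,000 runs) |
|---|---|---|---|
| 0.1 | 0.387 | 1.5% | 0.99% |
| 0.3 | 1.162 | 6.1% | 1.03% |
| 0.5 | 1.936 | 19.4% | 0.99% |

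*Masking (true fall of 1.3, opposing shift s)*

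| s | Net fall | Within arm detects | Between groups detects |
|---|---|---|---|
| 0 | 1.3 | 97% | 78% |
| 0.1 | 1.2 | 93% | 78% |
| 0.3 | 1.0 | 80% | 78% |
| 0.5 | 0.8 | 56% | 78% |

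**Precision given up.** With 80% power at alpha 0.01, the detectable effect is 1.33 SD of the change between groups (15 + 15) and 1.00 SD within arm (n = 15). The second figure holds only when s = 0, which a single arm cannot check.

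**The case against.** The best reply is that the controlled contrast is already in the plan. Section III collects untreated sputum, and the only Phase II test named anywhere is the between-group one. Before-after wording in an aim may simply describe the measurement; the TSLP outcome is itself a change over time, compared with no treatment. The general text on miRNA (in Statistical Analysis and again in III.2) leaves differential expression to the genomics core, with t tests or biochip algorithms, and prescribes no uncontrolled test. The array work is called exploratory and the study a pilot.

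Much of this stands. A reader might infer that Phase II is single-arm, that its primary analysis is uncontrolled, or that every target other than TSLP lacks a control. The documents do not support any of these: TSLP is compared between randomised groups, and the epithelial array sentence can fairly be read the same way. Nor does the plan commit to a paired test.

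What does not stand is the idea that the general miRNA text closes the gap. It names no Phase II comparator, so SA3.a remains the only stated comparison for miRNA and non-epithelial RNA. The exploratory label sits on the epithelial array goal, while Aim 3 is framed as a hypothesis to be tested, and exploratory sorting of markers still needs a valid contrast.

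**Conclusion.** The point holds in a limited form and should be fixed. The two descriptions of Phase II conflict, and for miRNA and non-epithelial RNA the only comparison stated is uncontrolled. This rests on the text alone.

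The size is illustrative, since the shifts, the paired test, and n and alpha for these targets are all assumed or borrowed. On false positives the problem is slight at 0.1 SD (1.5% against 1%) and material at 0.3 to 0.5 SD (6% to 19%). A reader might infer that masking is also serious from 0.3 SD. The figures do not show that: at 0.3 SD the within-arm test still detects 80%, against 78% between groups, and it falls clearly behind only at about 0.5 SD (56% against 78%). None of this touches the TSLP test.

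**What to change.** 1. In Specific Aims and under Specific Aim 3, reword the hypothesis and SA3.a as the 2-week change from baseline in RNA targets, compared between asthmatic participants (IA and AA) randomised to inhaled corticosteroid and those randomised to no treatment.
2. Align the SA3.a procedures with section III.1: fluticasone or no treatment, repeat sputum at 2 weeks in both groups, and a single dose.
3. Add to III.2: *The steroid effect on every RNA target assayed in Phase II (mRNA and miRNA, in each sorted cell population) is estimated from the between-group difference in 2-week change, by t-test, Wilcoxon test or the array algorithms already allowed. Within-group changes are descriptive only. A non-significant difference is not taken as proof of steroid resistance.* The last sentence is needed because, at 15 + 15 and alpha 0.01, a true 1.3 SD effect is missed in 22% of studies (1 − 0.78).

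**Cost.** No extra participants, visits or sputum samples. Precision is lower, as shown in the working. If untreated samples were not already due to be assayed, each untreated participant adds two chips per array type and cell population. With 15 untreated that is 15 × 2 = 30 for one population and 60 for two. If the 40 planned for Phase II were split equally (an assumption), it is 20 × 2 = 40 and 80. The plan itself notes that chips are expensive, so the number of populations arrayed should be settled at the same time.
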